3.1.5.3 Extent of Exposure to Study Medication

Participant exposure to study medication (in mg/kg, using baseline weight) will be collected and assessed from baseline to Week 16 and from baseline to Week 36. Exposure will be calculated as (last dose date of IP – first dose date of IP + 1).

In relation to the OCS use, for summary tables, exposure in mg/kg will be converted to prednisone equivalents / kg using the following conversion table:

Table 4. Conversion of Total Corticosteroid to Prednisone Equivalent

Systemic Corticosteroid (SCS)	Approximate equivalence dose (mg)
Prednisone	10
Prednisolone	10
Cortisone	50
Hydrocortisone	40
Methylprednisolone	8
Triamcinolone	8
Betamethasone	1.2
Budesonide	2.25
Dexamethasone	1.5
Deflazacort	12

3.1.6 Last contact

Last contact with the participant is defined as the latest of the below dates of assessments:

- Date of visits (on-site or home visits, remote audio or telephone visits)
- Date of randomization
- Start and end dates of dosing
- Date of disease state and BPDAI assessment
- Date of collection of laboratory evaluations
- Date of vital sign testing
- Date of physical examinations
- Date of ECGs
- Start and end dates of concomitant medications
- Start and end dates of hospitalization
- Start and end dates of AE

Dates of contact with the participant or dates of completion/discontinuation are not included. However, if at least one assessment among the ones reported above has occurred on the same date, the date of contact or completion/discontinuation will be indirectly included.

3.2 Primary outcome variable

The primary outcome variable is a binary response whereby participants will be classified as responders if they are in complete remission while off OCS for ≥ 2 months at Week 36. Otherwise, participants will be classified as non-responders.

Investigators will be asked to make a clinical assessment of the participants to determine their BP disease state (ie, active disease, disease control, end of consolidation phase, remission, and relapse) from Visit 2 until the end of the double-blind period, during the OLE period, and then in addition at the IP Discontinuation (IPD), End of Treatment (EOT) and follow-up visit.

At each visit, Investigators will be required to assess a participant's outcome measures, including the states defined in Table 4. The outcome measure will be documented in the eCRF.

Table 4 Definitions for Bullous Pemphigoid Outcome Measures

Outcome measure	Definition ^b
Disease control/beginning of consolidation phase	The time at which new lesions cease to form and established lesions begin to heal or pruritic symptoms start to abate
End of consolidation phase	Time at which no new lesions have developed for a minimum of 2 weeks and approximately 80% of lesions have healed and pruritic symptoms are minimal
Sustained partial remission on minimal steroid ^a /off steroid therapy	The presence of transient new lesions that heal within 1 week while the participant is on minimal steroid therapy or off steroid therapy for at least 2 months
Sustained complete remission on minimal steroid ^a /off steroid therapy	The absence of new or established lesions or pruritus while the participant is on minimal steroid therapy/off steroid therapy for at least 2 months
Relapse	The appearance of 3 or more new lesions per month (blisters, eczematous lesions, or urticarial plaques) or at least one large (> 10 cm diameter) eczematous lesion or urticarial plaques that do not heal within 1 week, or the extension of established lesions or daily pruritus in participants who have achieved disease control

^b Minimal steroid therapy is defined as less than or equal to 0.1 mg/kg/day of prednisone or equivalent

^c Definitions as per [Murrell et al 2012](#)

Each BP disease state clinical assessment collected during any scheduled/ unscheduled/ IPD/ EOT/ follow-up visits will be included in the Week 36 visit as per adjusted defined visit window, see Section [3.1.4](#), and analysed accordingly.

The primary endpoint is the proportion of participants who are in complete remission while off OCS for ≥ 2 months at Week 36.

A participant will be considered in complete remission for ≥ 2 months at Week 36 if a complete remission is recorded in the disease status eCRF at the clinical assessment which is assigned to the Week 36 visit when applying the windowing rules described previously, and a complete remission is recorded at least 55 days prior to this Week 36 date, and all evaluable disease states that are recorded during the 55 days between these assessments (ie, overall 8 weeks) are complete remission.

The disease state at each visit will be recorded on the eCRF form collecting the date of assessment and the disease state. A disease state clinical assessment reported in the eCRF as “Not Evaluable” will be considered as missing. Between two consecutive non-missing disease state assessments it will be assumed that the disease state collected at the first assessment is

current until the day before the second disease state assessment, unless intercurrent events happen. The same rule will be applied for two non-consecutive non-missing disease state assessments at windowed visits if at least one missing assessment is detected between them.

A participant will be considered off OCS for ≥ 2 months at Week 36 if off OCS on the day of the clinical assessment which is assigned to the Week 36 visit when applying the windowing rules and on the 55 days (ie, overall 8 weeks) before that date. Further details on the definition of day off OCS are contained in Section [3.1.5.1](#).

A participant will be considered in complete remission while off OCS for ≥ 2 months at Week 36 if both the definitions above are met.

Note that regardless of prior OCS use, participants who have been in complete remission while off OCS for ≥ 2 months at Week 36 will be classed as responders. For example, if participants require an increase in OCS dose after previously achieving disease control but they still taper and achieve the remission criteria by Week 36, this will be counted as response in the analysis. It is considered unlikely that this situation would emerge often, but given the clinical relevance of still being able to achieve remission and that OCS use is built into the remission definition, it is considered appropriate to count this situation as response in the analysis.

Intercurrent events for this estimand are unfavorable outcomes and will be handled with a composite strategy. The set of intercurrent events consists of participants who receive medications deemed to be intercurrent events as per Section [3.1.5.2](#) and participants who withdraw from the study. The primary estimand will regard these participants as non-responders from the time such events occur up to Week 36.

Participants who withdraw from the study will be considered non-responders starting after the last available non-missing BP disease state clinical assessment.

Participants who receive medications deemed to be intercurrent events as per Section [3.1.5.2](#) will be considered non-responders starting from the date of start of restricted medications. Missing/partial start dates are not allowed for restricted medications.

Participants with missing data at Week 36 for any other reason will be considered as non-responders.

The amount of missing data for this study is expected to be low, as participants who prematurely discontinue IP will be asked to come in for all visits and complete all study assessments up to the end of the study.

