To compare the effect of benralizumab with placebo on clinical efficacy in participants with symptomatic BP up to Week 16	
 
Key secondary a Cumulative OCS exposure (mg/kg) from baseline to Week 16.
 
Proportion of participants who remain relapse-free up to Week 16.
 
Proportion of participants with any clinical benefit (eg, partial and complete remission during taper, with no steroid use, or with minimal steroid use [ie, <math>< 0.1</math> mg/kg/day]) at Week 16.
 
Time to disease control, OCS dose (mg/kg) at disease control and time to the end of the consolidation phase.
 
Change from baseline in BPDAI activity score at Week 16.
 
Change from baseline in BPDAI-Pruritus score at Week 16.
 

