**Table 6 Definitions for Bullous Pemphigoid Outcome Measures**

Outcome measure	Definition b
Disease control/beginning of consolidation phase	The time at which new lesions cease to form and established lesions begin to heal, or pruritic symptoms start to abate
End of consolidation phase	Time at which no new lesions have developed for a minimum of 2 weeks and approximately 80% of lesions have healed and pruritic symptoms are minimal
Sustained partial remission on minimal steroid a /off steroid therapy	The presence of transient new lesions that heal within 1 week while the participant is on minimal steroid therapy or off steroid therapy for at least 2 months
Sustained complete remission on minimal steroid a /off steroid therapy	The absence of new or established lesions or pruritus while the participant is on minimal steroid therapy/off steroid therapy for at least 2 months
Relapse	The appearance of 3 or more new lesions per month (blisters, eczematous lesions, or urticarial plaques) or at least one large (> 10 cm diameter) eczematous lesion or urticarial plaques that do not heal within 1 week, or the extension of established lesions or daily pruritus in participants who have achieved disease control

a Minimal steroid therapy is defined as less than or equal to 0.1 mg/kg/d of prednisone or equivalent

Definitions as per [Murrell et al 2012](#)

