## BP Remission

BP remission (see [Table 6](#) for definition) will be assessed at each study visit per the SoA ([Table 2](#)). Remission can be partial or complete and can occur off steroid therapy or on minimal steroid therapy.

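### Table 6 builds 2 months into complete remission and SAP 3.2 adds a 55-day look-back, so the duration can be counted twice and primary response can depend on how a site reads the table

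*SAP*

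**What the plan says.** **Definition given to sites.** Protocol 8.1.1.1 has the investigator code a disease state at each visit and keeps the participant in active disease until a Table 6 state is reached. The BP Remission paragraph points to Table 6 for the definition. SAP 3.2 repeats the instruction for its own copy of the table: "Investigators will be required to assess a participant's outcome measures, including the states defined in Table 4". The only complete-remission row, identical in both documents, is the sustained one: "The absence of new or established lesions or pruritus while the participant is on minimal steroid therapy/off steroid therapy for at least 2 months". A footnote adds: "Minimal steroid therapy is defined as less than or equal to 0.1 mg/kg/d of prednisone or equivalent".

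**Primary derivation (SAP 3.2).** The remission leg needs complete remission in the eCRF at the Week 36 assessment, an earlier record ("a complete remission is recorded at least 55 days prior to this Week 36 date"), and complete remission at every evaluable assessment in between. The steroid leg needs the participant off OCS on the assessment day and "on the 55 days (ie, overall 8 weeks) before that date". The legs are then joined: "A participant will be considered in complete remission while off OCS for ≥ 2 months at Week 36 if both the definitions above are met".

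**Sections that use a visit-day meaning.** The Week 16 objective in Protocol Table 1 counts "partial and complete remission during taper, with no steroid use, or with minimal steroid use", and Protocol 9.4.2.3 summarises remission in those same categories. SAP 3.4.6 takes the investigator's remission call at Week 16 with no duration and only then splits it by OCS use. SAP 3.4.2 has a rule for participants still taking OCS on the date complete remission is recorded.

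**The concern.** A site that follows the table makes its first complete-remission entry when 2 months have already passed. SAP 3.2 treats that entry as the start of the 2 months. A site that codes what it sees on the day makes the entry earlier, and the program then measures the 2 months once, as the endpoint's name implies.

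Take a participant who is free of lesions and itch on minimal OCS from Week 24, off OCS by Week 28, and clear through Week 36. This participant meets the stated endpoint. With visit-day coding, complete remission is on record at Week 28 and the participant is a responder. With table coding, the first possible record is about Week 32, and SAP 3.2 returns a non-responder. The skin, itch and steroid history are the same, yet the primary outcome differs.

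The participants affected are those who taper late or a second time. Protocol 9.4.2.1 and SAP 3.2 both say that someone who needed more OCS after disease control should still count as a responder if the criteria are met by Week 36.

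**Working it through.** **Inputs.** Table duration: at least 2 months, taken as 56 days (the SAP's 8 weeks) or about 61 calendar days. Minimal OCS: up to 0.1 mg/kg/day (Table 6). Look-back: 55 days (SAP 3.2). Scheduled Week 28 is Day 197 and Week 36 is Day 253 (SAP 3.1.4). Taper: 20% per week to 10 mg/day, then 2.5 mg every other week (Protocol 4.1.2 and 6.5.1). Assumptions: weights of 50 to 100 kg, starting OCS of 0.5 or 0.75 mg/kg/day, first cut on the taper start day, participant clear from the first minimal dose, no relapse.

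**1. The SAP's own figure.** 55 + 1 = 56 days = 8 weeks, as stated. Day 253 − Day 197 = 56, so a record at the scheduled Week 28 visit satisfies the look-back. The latest day for the earlier record, and the first day that must be off OCS, is 253 − 55 = Day 198.

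**2. Both rules applied as written.**
- Total: 56 + 56 = 112 days, or 61 + 56 = 117 days. Dividing by 30.44 gives 3.7 and 3.8 months.
- Minimal OCS needed by: 198 − 56 = Day 142 (Week 20.1), or 198 − 61 = Day 137 (Week 19.4).
- The off-OCS leg is unchanged at 56 days.

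**3. One taper, 70 kg at 0.5 mg/kg/day (35 mg).** Doses at taper Weeks 0 to 5: 28, 22.4, 17.9, 14.3, 11.5, 10 mg. Then 7.5 mg at Week 7, 5 mg at Week 9, 2.5 mg at Week 11 and zero at Week 13. The minimal threshold is 70 × 0.1 = 7 mg, first met at Week 9.
- Visit-day coding: off by Week 28, so latest start 28 − 13 = Week 15.
- Table coding with 2 months as 8 weeks: minimal by Week 20, so latest start 20 − 9 = Week 11.

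**4. Shift across weights.** Shift = (28 − weeks to off) − (20 − weeks to minimal) = 8 − (weeks from first minimal dose to off). Below 10 mg that interval depends only on the first qualifying dose:

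| Weight | First qualifying dose | Weeks from it to off | Shift |
|---|---|---|---|
| 50–70 kg | 5 mg | 4 | 4 weeks |
| 80–90 kg | 7.5 mg | 6 | 2 weeks |
| 100 kg | 10 mg | 8 | 0 weeks |

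Taking 2 months as 61 days adds 5 days (0.7 week) to each shift.

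**5. On the visit grid.** Ten cases (50, 60, 70, 80, 100 kg at both doses; 2 months as 61 days):

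| Taper start | Result |
|---|---|
| Weeks 4, 6, 8 | all ten pass both readings |
| Week 10 | three of ten fail only under table coding |
| Week 12 | eight fail only under table coding, one passes both, one fails both |

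**6. Consistency with Week 16.** Table-coded complete remission at Day 113 needs minimal OCS by 113 − 61 = Day 52 (Week 7.3). With tapers starting at Week 4 or later, the earliest modelled minimal dose is at Week 11. The planned Week 16 complete-remission summary would be nearly empty, which suggests its authors had the visit-day meaning in mind.

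**7. Response rates.** The documents give neither the share of participants tapering late nor the coding sites use, so no change in the 50% and 20% planning rates can be calculated.

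**The case against.** The strongest reply is that the double count depends on a form not among the documents. SAP 3.2 scores what the eCRF holds and calls the entry complete remission, without the word sustained. The list of visit states in both documents says simply remission, and investigators are to assess measures *including* the table's states, which is not exhaustive wording. The Week 16 endpoint, SAP 3.4.2 and SAP 3.4.6 all work naturally with a visit-day state, and SAP 3.2 itself derives duration from successive records plus steroid dates. The table is also ambiguous: the 2 months may qualify only the off-steroid branch. The BP Remission paragraph says "Remission can be partial or complete and can occur off steroid therapy or on minimal steroid therapy" and gives no duration.

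Much of this stands. A reader might infer that the endpoint requires 4 months in place of 2, or 4 months off OCS. The documents do not support either. The longer period arises only under table coding, and the added time may be on minimal OCS. A reader might also infer that response rates must fall below plan and power be lost. Protocol 9.2 and SAP 1.3 extrapolate the 20% from relapse-free proportions in another trial, without naming a 2-month rule in that step, and nothing in the text sizes a fall.

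The planned timetable also limits exposure. Off OCS at 4 to 5 months after a 3 to 4 month taper puts taper start near month 1, well inside the range that passes either way. Because coding is blinded, differences between sites would blur the endpoint and would not in themselves favour an arm.

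The reply does not remove the conflict. The visit-day meaning has to be inferred from secondary endpoints, while the one definition sites are sent to says 2 months.

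**Conclusion.** The definition and the derivation conflict, and this bears on primary responder status. Followed together as written, they require about 112 to 117 days clear on minimal or no OCS, against the 56 days SAP 3.2 intends. With visit-day coding the requirement is 56 days. The documents do not say which applies.

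The practical reach is limited to late or repeat taperers. The latest qualifying taper start moves earlier by 0 to 4 weeks over the modelled 50 to 100 kg, and starts up to about Week 8 are unaffected. These figures rest on the protocol taper, the assumed weights and doses, and sustained clearance. How many participants fall in the affected band, and what that does to either arm's rate, cannot be derived. The case for acting is that the primary outcome should not turn on a site's choice between two readings.

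**What to change.** Before unblinding, state in Protocol Table 6, SAP Table 4 and the eCRF completion guide what a *complete remission* entry means, and choose one:

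- **Visit-day state:** no new or established lesions and no pruritus at this visit. Keep the SAP 3.2 look-back and say that the program derives the 2 months.
- **Already sustained state:** drop the 55-day prior-record requirement. Require sustained complete remission at Week 36 plus 56 days off OCS.

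Make SAP 3.4.1, 3.4.2 and 3.4.6 consistent with the choice. SAP 3.4.2 counts time from the recorded date, so under table coding it could miss up to about 8 weeks.

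Run a blinded query of visits with BPDAI activity 0 and a 24-hour itch item of 0 that are not coded as complete remission. Do not use the BPDAI-Pruritus total for this: it includes past-month itch (Protocol 8.1.2.3) and would miss newly clear participants.

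Cost: one clarification to sites, small edits to the table and SAP, and one blinded query round. Entries already made may need recoding so that old and new coding are not mixed. No new assessments are needed.

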### **1.3 Schedule of Activities**

The Schedule of Activities (SoA) at each visit for this study is provided in [Table 2](#). Details of the schedule of at-home and site visit patient-reported outcome (PRO) assessments are provided in [Table 3](#).

**Table 2** Schedule of Activities

Study period	Screening	Double-blind treatment period													OLE			IPD/ EOT c	FU (12 wks after last dose of IP)	UNS d	Details in CSP section
		V2	V3	V4	V5	V6	V7	V8	V9	V10	V11	V12	V13/ EOT a	Every 4 wks (V14 to V22) b	V19	Every 12 weeks (From V23)					
Visit	V1	0	2	4	6	8	12	16	20	24	28	32	36	40-72	60	From Week 76					
Week (Wk)																					
Visit window (days)	(Target 0-4 days)	±3	±3	±3	±3	±3	±3	±3	±3	±3	±3	±3	±3	±7	±7	±7	±7	±7			
General Procedures																					
Informed consent	X																				Appendix A 3
Demography/medical history	X																				Sections 5.1 and 5.2
Inclusion/exclusion criteria	X	X																			Sections 5.1 and 5.2
Record concomitant medications, including OCS dose and compliance check e	X	X	X	X	X	X	X	X	X	X	X	X	X	X	X	X	X	X	X	Section 6.5	
Randomization		X																			Section 6.3.1

**Table 2** Schedule of Activities

Study period	Screening	Double-blind treatment period													OLE			IPD/ EOT c	FU (12 wks after last dose of IP)	UNS d	Details in CSP section
Visit	V1	V2	V3	V4	V5	V6	V7	V8	V9	V10	V11	V12	V13/ EOT a	Every 4 wks (V14 to V22) b	V19	Every 12 weeks (From V23)					
Week (Wk)		0	2	4	6	8	12	16	20	24	28	32	36	40-72	60	From Week 76					
Visit window (days)	(Target 0-4 days)	±3	±3	±3	±3	±3	±3	±3	±3	±3	±3	±3	±3	±7	±7	±7	±7				
Disease Measurements																					
Disease state, BPDAL IGA, and CCI	X	X	X	X	X	X	X	X	X	X	X	X	X	CCI					Sections 8.1.1.1, 8.1.1.2, 8.1.1.3, and 8.1.1.4		
CCI								X						X	X e				Section 8.1.1.5		
		X												X					Section 8.1.1.6		
Healthcare resource utilization		X	X	X	X	X	X	X	X	X	X	X	X	X	X	X	X	X	Section 8.1.1.7		
PRO Procedures																					
Distribution of handheld device and instruction on use h		X																	Section 8.1.2		

**Table 2** Schedule of Activities

Study period	Screening	Double-blind treatment period													OLE			IPD/ EOT c	FU (12 wks after last dose of IP)	UNS d	Details in CSP section

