1.3 Number of subjects

Approximately 140 participants will be enrolled/screened in order to achieve approximately 100 eligible study participants randomly assigned to study intervention.

The sample size calculation was derived for the primary endpoint, the proportion of participants who are in complete remission while off OCS for ≥ 2 months at Week 36.

Approximately 50 participants are needed per treatment group to detect a 30% difference between benralizumab and placebo with 85% power. The calculation is based on a 2-sided test and a 5% significance level and assumes a response rate of 50% for benralizumab and 20% for placebo.

There is limited evidence currently available from completed comparative BP trials to date to base the study size assumptions on. However, a mepolizumab Phase 2 trial with a similar participant population, design, and steroid taper rate reported a low proportion of patients relapse free up to 36 weeks (20% versus 33% for mepolizumab versus placebo; [Simon et al 2020](#)). From this study, the assumption that an expected remission rate off steroids at Week 36 would be low, at most 20%, was extrapolated. A 30% improvement in this remission rate was recommended by a panel of BP experts to be at the lower end of what may be clinically meaningful, and so was considered to be a conservative assumption.

A non-binding interim futility analysis will be performed by an Independent Data Monitoring Committee (IDMC) when approximately 36 randomized participants (ie, when approximately 36% of the total amount of statistical information is available) have had the opportunity to complete at least 36 weeks of follow-up. By conducting the interim analysis, the overall power will not be affected substantially. Full details are provided in Section [5](#).

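### SAP 3.2 can be read so that a non-remission recorded at an on-schedule Week 28 visit, 56 days before Week 36, is not checked in the primary endpoint

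*SAP*

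**What the plan says.** SAP 3.2 (Primary outcome variable) sets three conditions for complete remission (CR) lasting at least 2 months at Week 36:

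1. CR at the assessment assigned to Week 36.
2. An earlier CR, with no limit on how early: "a complete remission is recorded at least 55 days prior to this Week 36 date".
3. No other state in between: "all evaluable disease states that are recorded during the 55 days between these assessments (ie, overall 8 weeks) are complete remission".

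The same section then gives a carry-forward rule. Where two non-missing assessments follow one another, the earlier state is treated as "current until the day before the second disease state assessment, unless intercurrent events happen".

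A separate condition requires the participant to be off oral corticosteroids (OCS) on the Week 36 assessment day and "on the 55 days (ie, overall 8 weeks) before that date".

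The visit-window table in SAP 3.1.4 schedules Week 24 on study day 169, Week 28 on day 197, Week 32 on day 225 and Week 36 on day 253. The protocol's Schedule of Activities allows double-blind visits to vary by 3 days either way.

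**The concern.** Condition 2 does not require the earlier CR to be the last state recorded before the two-month period begins. Condition 3 refers to 55 days, and an on-schedule Week 28 visit lies one day outside that span. A participant could therefore satisfy condition 2 with an older CR, lapse at Week 28, recover by Week 32, and still pass a programmed check of the last 55 days.

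The primary endpoint credits complete remission only. Partial remission is credited in a separate secondary endpoint (SAP 3.4.1). Under this reading, a participant in partial remission at the start of the two-month period, and observed in CR for only the last four weeks, would be a primary responder. The section's other wording makes the same participant a non-responder. If the choice is left to programming, the primary endpoint is not fully specified.

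**Working it through.** **Reproducing the plan's figure.** The 55 days before Week 36 plus the Week 36 day: 55 + 1 = 56 days; 56 / 7 = 8.0 weeks. This agrees with the stated 8 weeks.

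**Where Week 28 falls.** 253 - 197 = 56, so planned Week 28 is day -56. A fixed look-back of days -55 to -1 is study days 198 to 252. Of the scheduled visits, it contains only Week 32 (day 225, day -28).

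**Test case.** Off OCS on days 198 to 253, no unscheduled disease-state record in that span, and these states:

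| Visit | Study day | Relative to Week 36 | State |
|---|---|---|---|
| Week 24 | 169 | -84 | CR |
| Week 28 | 197 | -56 | Partial remission |
| Week 32 | 225 | -28 | CR |
| Week 36 | 253 | 0 | CR |

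Condition 1 is met, and condition 2 is met by Week 24 (84 days back). Condition 3 depends on the reading:

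- **A. Fixed look-back, recorded states only.** The only record in days 198 to 252 is the Week 32 CR. Result: responder.
- **B. All records between the earlier CR and Week 36.** The interval from day 169 to day 253 contains the Week 28 partial remission. Result: non-responder.
- **C. Daily state with carry-forward on days -55 to 0.** Partial remission is in force on days 197 to 224 (28 days), of which days 198 to 224 (27 days) are inside the look-back. Result: non-responder.

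**Controls.** With no CR before the Week 28 lapse, all three readings give non-responder, because condition 2 fails. With CR at Weeks 28, 32 and 36, all three give responder. With a lapse at Week 32, all three give non-responder. The readings part only when a CR precedes a Week 28 lapse.

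**Visit windows, under reading A.** Let *a* and *b* be the shifts of Week 28 and Week 36, each from -3 to +3. The gap is 56 + *b* - *a*, which ranges from 50 to 62 days over 7 x 7 = 49 date pairs:

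- 56 days or more (*b* >= *a*), Week 28 outside the check: 28 pairs, including the planned schedule.
- Exactly 55 days: 6 pairs.
- Fewer than 55 days, Week 28 inside the check: 15 pairs.

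**Weight of one participant.** SAP 1.3 plans about 50 per group: 1 / 50 = 2 percentage points.

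**The case against.** The strongest reply is that the text already excludes this participant. Strictly between planned Week 28 (day 197) and planned Week 36 (day 253) lie days 198 to 252, which is exactly 55 days. The wording therefore fits that pair, with Week 28 as the earlier assessment that must itself be CR. If an older CR is used, Week 28 lies between the two assessments and fails condition 3. The carry-forward rule also puts partial remission inside the window.

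Much of this stands. A reader might infer that the SAP definitely counts this participant as a responder. It does not: that follows under one of three readings. Nor would it be right to say that the wording works only when the earlier CR is exactly 55 days back.

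The reply does not remove the ambiguity. With a Week 24 CR the interval between assessments is 84 days, which does not match the 55 days and 8 weeks stated in the same sentence. Condition 3 speaks of recorded states, not states assumed current. SAP Section 6 describes the Section 3.2 addition as dealing with missing assessments between non-missing ones, and in the test case none is missing. A programmer could reasonably code reading A.

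Other rules narrow the pattern. A lapse treated with OCS inside the window fails the off-OCS condition, and treatment with a restricted medication listed in SAP 3.1.5.2 makes the participant a non-responder. What remains is a lapse managed without either. Partial remission, defined by transient lesions that heal within a week, can be such a lapse.

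**Conclusion.** The point holds as an ambiguity in the primary endpoint rule: the same section supports opposite classifications of one participant, and one of them credits two months of CR to someone observed in CR for four weeks.

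It requires a CR before Week 28, a non-remission at Week 28 managed without OCS in the window or a listed restricted medication, and CR at every later record. The documents give no frequency for this pattern; it is probably low. Each affected participant is worth 2 points in an arm of 50.

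A reader might take 28 of 49 (57%) as a misclassification rate. It is only a count of compliant date pairs under reading A; as a probability, even of visit timing, it would need uniform and independent visit dates, which the documents do not state. Under readings B and C the lapse is seen whatever the dates. The rule applies to both arms alike, and no effect on power, type I error or the direction of the treatment estimate has been shown.

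**What to change.** Before unblinding, replace the third condition in SAP 3.2 with a sentence to this effect:

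> The last evaluable disease state on or before day -55 (55 days before the assessment assigned to Week 36), and every evaluable state after it up to and including that assessment, must be complete remission. The carry-forward rule in this section applies to this criterion.

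In the test case the last state on or before day -55 (study day 198) is the Week 28 partial remission, so the participant is a non-responder. With CR at Week 28 the participant remains a responder. The remission period then matches the off-OCS window, days -55 to 0.

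The cost is one sentence and one programming condition, with no change to study conduct. The observed response rate may be slightly lower. This includes the date pairs in which Week 28 falls fewer than 55 days before Week 36: there the preceding state, normally Week 24, must be CR, and an older CR no longer suffices.
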